7.1.2 Laboratory Test Abnormality

Laboratory test results will be recorded, or appear on the laboratory reports submitted directly from the central laboratory. Out of range laboratory test values should not be reported as AEs unless they are considered to be clinically significant abnormalities by the Investigator.

7.1.3 Adverse Events of Special Interest (Infusion-Associated Reactions)

IARs will be considered AEs of special interest. Any AE that occurs during the infusion or within 4 hours after the infusion is completed and is assessed by the Investigator as at least possibly related to study drug will be designated as an IAR for this study. In addition, if, at any time during the study, the Investigator observes symptoms that he/she considers to be consistent with an IAR or hypersensitivity reaction related to administration of study drug, the symptoms should be recorded as an AE(s) and designated as an IAR(s). Individual adverse event terms should be recorded rather than the terms IAR or infusion associated reaction.

As with any ERT, medications and equipment for the treatment of hypersensitivity reactions must be available for immediate use in case of unexpected, severe hypersensitivity reaction. These supplies include, but are not limited to, oxygen, acetaminophen, antihistamines (eg, diphenhydramine, parenteral and oral), corticosteroids, epinephrine, and cardiopulmonary resuscitation devices.

General guidelines for classifying the severity of a reaction are provided in Section 7.1.1

For similar biological products, most acute IARs occur within 2 hours of the infusion. Signs of a possible acute IAR may include:

• Hyperemia (flushing), fever and/or chills, nausea, pruritus, urticaria, gastro-intestinal symptoms (vomiting, diarrhea, abdominal cramping), cardiopulmonary reactions, including chest pain, cardiac arrhythmias, dyspnea, wheezing, stridor, hypotension or hypertension.

General guidelines for the diagnosis and management of IARs are provided in Table 9. These guidelines are not intended to be comprehensive. The Investigator should use clinical judgement in the management of IARs in individual subjects participating in this study. In the case of a severe life-threatening reaction, current medical standards for emergency treatment are to be followed.

Symptoms	Action
Mild Reaction Common • Hyperemia (flushing) • Lightheadedness • Nausea • Mild chest discomfort (tightness) Less Common • Fever and/or shivering • Palpitations • Headache • Irritability (especially in young children)	 Slow infusion rate by 50% Increase infusion time in accordance with institutional standard of care Administer oral anti-pyretic and/or antihistamine Once the event has resolved, the infusion should continue at reduced rate for a minimum of 30 minutes before infusion is increased to 75% of original rate Decrease infusion rate by a further 25% if symptoms persist If symptoms continue despite rate reduction, stop infusion Pre-treat with oral antihistamine and antipyretic prior (approx. 1.5 hours) to next infusion eg, diphenhydramine 25-50 mg by mouth and acetaminophen 650 mg by mouth
 Hyperemia (flushing) Chest discomfort Itching and/or raised urticarial rash Severe headache Gastrointestinal symptoms, vomiting, diarrhea, abdominal cramping 	 Give antihistamine intravenously and consider IV steroids in accordance with institutional standard of care Give any prescribed inhaler treatment if appropriate Collect serum for analysis of tryptase 1-3 hours after the IAR onset and another serum sample for tryptase and ADA during the next study visit (≥4 days after the IAR) prior to the infusion. Pre-treat with oral antihistamine and antipyretic prior to next infusion Skin testing may be considered
 Severe Reaction Clinically significant cardiovascular effects (hypotension defined as a decline approaching 20-30% of their preinfusion value without alternative etiology (agitation, pain, fluid overload, dehydration) Respiratory symptoms: Significant shortness of breath, stridor, wheezing, laryngeal oedema, swelling of tongue. Cardiac arrhythmias Anaphylactic/Anaphylactoid shock with hypotension and circulatory collapse 	 Stop infusion Give oxygen, if available Give intramuscular injection of epinephrine (adrenaline) Give antihistamines intravenously and steroids intravenously Collect serum sample for tryptase 1-3 hours after the IAR onset and another serum sample for tryptase and ADA during the next study visit (≥4 days after the IAR) prior to the infusion. Skin testing may be considered Dosing of the subject will be suspended until the SRC has completed review of the IAR, and any other relevant safety data (Section 6.2)

Table 9:Guidelines for the Management of IARs

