1.4 Clinical Data

1.4.1 Data for SBC-103

As this is a first-in-human study, no clinical data for SBC-103 were available when this study was planned and initiated.

As described in Section 3.1, subjects in Part A receive IV infusions of SBC-103 at 1 of 3 doses (0.3, 1, or 3 mg/kg) QOW for 24 weeks followed by a 4-week temporary interruption of therapy prior to re-initiating therapy at Week 28 in Part B. Modifications to dose or dosing frequency for individual subject(s) is permitted in Part B with the intent of treating subjects with the lowest potentially efficacious dose that is safe and tolerable.

As of 20 November 2015, preliminary data were available for all subjects enrolled in this study, including approximately 20 to 40 weeks (~11 to 20 QOW doses) of preliminary safety data, and preliminary PK and PD data through Week 12 (~7 QOW doses).

These data are briefly summarized below. *However, it should be noted that these are preliminary data from an ongoing study and an open database, and therefore, are subject to change based on data review, reconciliation, and/or auditing.*

As described in Section 3.1.1, approximately 9 subjects were to be enrolled in this study across 3 dose cohorts (n=3/cohort) with a provision to permit enrollment of additional subjects if more than 3 subjects in a cohort had entered Screening and were eligible to participate in the study. A total of 11 subjects were sequentially enrolled in this study into Cohort 1 (0.3 mg/kg, n=3), Cohort 2 (1 mg/kg, n=4), or Cohort 3 (3 mg/kg, n=4). All subjects had a confirmed diagnosis of MPS IIIB and documented developmental delay with onset before 6 years of age. The majority of subjects enrolled in this study are PPD and the mean (SD) age was 7.5 (2.82) years for subjects in the 0.3 mg/kg dose cohort, 6.6 (4.54) years for subjects in the 1 mg/kg dose cohort, and 4.5 (2.10) years for subjects in the 3 mg/kg dose cohort.

Page 28 of 121

As of 20 November 2015, all 3 subjects in Cohort 1 have completed Part A of the study and have received between 5 and 7 doses of SBC-103 at 1.0 mg/kg QOW in Part B; all 4 subjects in Cohort 2 have completed Part A and 2 of these subjects have received 2 doses at 3.0 mg/kg QOW in Part B; and the 4 subjects in Cohort 3 have completed between 20 and 24 weeks of Part A at 3.0 mg/kg.

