1.5.1.2 Part A (Initial Therapy): Dose Selection Rationale

Part A of this study is an open label, dose escalation study of 3 dose levels of SBC-103 (0.3, 1, and 3 mg/kg) administered by IV infusion QOW for 24 weeks. For a 7-year-old MPS IIIB patient weighing approximately 30 kg, the 3 dose levels of SBC-103 (0.3, 1, and 3 mg/kg) would equate to total doses of 9 mg, 30 mg, and 90 mg, respectively (Centers for Disease Control [CDC] Clinical Growth Charts, NGLU-CL01 Data on File).

The dose scaling across species for SBC-103 has used body weight. This is based on reviews of the approach taken for therapeutic proteins (Tang 2004, *J Pharm Sci*; Mahmood 2004, *J Pharm Sci*), particularly enzyme replacement therapies such as Elaprase[®].

The selection of 0.3 mg/kg as the starting dose of SBC-103 in Part A was based on: the NOAELs in the 3-month juvenile Cynomolgus monkey study and in the 4-week Sprague-Dawley rat study when SBC-103 was administered as an IV infusion, along with the pharmacologic effects observed in the NAGLU-deficient nonclinical mouse model of MPS IIIB and PK/PD modeling of nonclinical data.

In the Sprague-Dawley rat, the NOAEL was defined as 3 mg/kg based on the observed vascular/perivascular inflammation in the heart and lungs; this represents a 10-fold margin over the proposed starting dose (0.3 mg/kg) on a mg/kg basis. Transient clinical signs attributable to SBC-103 infusions were observed at a dose of 10 mg/kg, generally after the third and fourth

doses (see Section 1.3). Given the frequent presence of anti-SBC-103 antibodies, these likely reflect hypersensitivity to the administration of a human protein to a rat.

In the juvenile Cynomolgus monkey study, which is considered the most relevant study to support studying SBC-103 in the MPS IIIB pediatric population, the NOAEL was defined as 10 mg/kg QW and 20 mg/kg QOW. This represents a 33- and 66-fold margin over the proposed starting dose (0.3 mg/kg) on a mg/kg body weight basis.

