4 STUDY POPULATION

4.1 Target Population

The target population for this study is male and female subjects with documented MPS IIIB who are greater than or equal to 2 years old but less than 12 years old.

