6.2 Stopping Rules

6.2.1 Stopping Rules in Individual Subjects

During Part A (Initial Therapy), Part B (Therapy at 1 and/or 3 mg/kg), and Part C (Therapy at 5 and/or 10 mg/kg), subjects who experience a severe IAR, a serious or severe AE that is

Page 75 of 121

considered related to SBC-103, or a significant elevation in specific laboratory values will have SBC-103 dosing paused based on the rules described below.

For IARs:

- Subjects who develop a severe IAR, as defined in Section 7.1.3, must stop treatment until their information is reviewed by the SRC. Dosing with alterations to the infusion regimen (eg, pretreatment or slowing the rate of infusion) may resume once the SRC and the Sponsor approve.
- Subjects with mild or moderate IARs can continue receiving SBC-103 in the study. The SRC or Sponsor may recommend alterations to the infusion regimen (eg, pretreatment or slowing the rate of infusion).

For all other AEs (ie, AEs that are not characterized as IARs):

- Any event considered related to SBC-103 which is either serious or severe will result in pausing additional dosing in an individual subject. The SRC and the Sponsor will review the data and will resume dosing only after review and agreement.
- Subjects with mild or moderate non-serious AEs can continue receiving SBC-103 in the study.

For Laboratory Values:

- Dosing will be paused based on confirmed elevations in AST or ALT under the following circumstances:
 - In the event that a subject's AST or ALT is greater than or equal to 2 times the ULN (when baseline ALT or AST was within normal limits)
 - In the event that a subject's AST or ALT is greater than or equal to 3 times the ULN (if baseline ALT or AST greater than 1.5 ULN).

Dosing will only resume after AST or ALT have returned to baseline or to study nadir (nadir values may be confirmed by additional lab sampling at the discretion of the investigator, using the same lab for analysis of each sample), or normalized if the baseline level was within normal limits.

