7.2.3 Treatment and Follow-up of Adverse Events

During the study, all AEs and SAEs will be followed up until they have returned to baseline status or stabilized or until the Investigator and Sponsor or designee agree that follow-up is no longer necessary. If a clear explanation is established, it should be documented.

Treatment of AEs is at the discretion of the Investigator and should follow the standards of medical care at the Investigator's institution.

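### Table 9's pre-treatment example after a mild infusion reaction prints flat drug amounts, with no weight or age basis, in a study of children (minor safety wording)

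*Protocol*

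**What the plan says.** Table 9 in Protocol Section 7.1.3 gives guidance on managing infusion-associated reactions (IARs) by severity. The mild-reaction row ends with pre-treatment about 1.5 hours before the next infusion. Its examples are oral diphenhydramine 25-50 mg and "acetaminophen 650 mg by mouth". The row between mild and severe carries essentially the same step without naming a drug or an amount: "Pre-treat with oral antihistamine and antipyretic prior to next infusion".

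The study population (Section 4.1) is "male and female subjects with documented MPS IIIB who are greater than or equal to 2 years old but less than 12 years old"; Section 4.3.1 applies that age range at consent. Acetaminophen is also named in Sections 1.5.2 and 7.1.3, among the supplies to keep at hand, without a dose. Nothing elsewhere supplies a weight, age or maximum qualifier for the Table 9 amounts.

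Three provisions soften the line:

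- The text above Table 9 calls its contents general and not comprehensive, and adds: "The Investigator should use clinical judgement in the management of IARs in individual subjects participating in this study".
- Section 7.2.3 states: "Treatment of AEs is at the discretion of the Investigator and should follow the standards of medical care" at the site's institution.
- Section 6.2.1 lets the Safety Review Committee (SRC) or the sponsor recommend pretreatment after a mild or moderate IAR.

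**The concern.** A flat amount gives the smallest child the largest dose per kg. Elsewhere the protocol adjusts drugs to the child. Study drug is prepared from the latest scheduled weight, to 0.1 kg (Section 6.6.1), and the propofol guidance is per kg, with a bolus that depends on age (Section 5.2.3). The mild row prints two amounts with no such basis, in a table that staff would consult when planning the infusion after a reaction.

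What is at stake is the suitability of a supportive-care example for young children. The primary safety endpoint, the dose-escalation decisions and the SAP's summaries do not depend on this line.

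**Working it through.** **Inputs**

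- Acetaminophen example: 650 mg, one amount (Table 9, mild row).
- Diphenhydramine example: 25-50 mg (same line).
- Reference weight: Section 1.5.1.2 takes as its example "For a 7-year-old MPS IIIB patient weighing approximately 30 kg". This is the only body weight that the documents give for a child.
- Number of children enrolled: 11 (Section 1.4.1).

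**Check of the reference weight.** Section 1.5.1.2 converts its three dose levels to total amounts for that child: 30 × 0.3 = 9 mg, 30 × 1 = 30 mg and 30 × 3 = 90 mg. These match the printed figures, so 30 kg is the protocol's own working weight.

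**Amount per kg = flat amount / body weight.** Only the 30 kg row uses a weight from the documents. The others are assumptions that show the direction.

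| Weight | Acetaminophen, mg/kg | Ratio to 30 kg | Diphenhydramine, mg/kg |
|---|---|---|---|
| 40 kg (assumed) | 650/40 = 16.3 | 0.75 | 0.63 to 1.25 |
| 30 kg (protocol) | 650/30 = 21.7 | 1.0 | 0.83 to 1.67 |
| 25 kg (assumed) | 650/25 = 26.0 | 1.2 | 1.00 to 2.00 |
| 20 kg (assumed) | 650/20 = 32.5 | 1.5 | 1.25 to 2.50 |

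The diphenhydramine range is two-fold, so using its lower end offsets a halving of body weight and no more. It leaves some room for adjustment, but it is not scaled to weight or age either. Both drugs therefore belong in the point.

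**What cannot be computed.** The documents give no weight for any enrolled child, no per-kg limit for either drug and no count of mild IARs followed by pre-treatment. An excess over a limit cannot be calculated from them, and neither can the number of children exposed.

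**The case against.** The strongest reply is that no standard in the documents is breached. Dividing a fixed amount by weight shows only that the per-kg amount varies, and calling it too high needs a pediatric limit that the documents do not contain. The line is also introduced as an example, inside guidance that defers to clinical judgement and to institutional practice.

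There are further safeguards. Every IAR, serious or not, reaches the sponsor within 24 hours (Sections 7.2.1 and 7.4.1). Infusions are at least 10 days apart (Section 6.1 and the assessment schedules), so the sponsor should know of a reaction before the next pre-treatment. Section 4.4 has the dose of each concomitant medication recorded. The neighbouring row's silence on amounts does not prove the mild row wrong, and that row omits the 1.5-hour lead time as well.

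Most of this stands, and it sets the severity. It does not remove the point. None of these texts supplies a weight basis for the planned amount, and Section 7.2.3 speaks of treating events rather than of preventing the next one. The protocol prints an actual amount here. An example in a pediatric protocol should suit every child it covers, and this one cannot do so without adjustment.

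**Conclusion.** The point holds as a minor correction of safety wording. Both example amounts in the mild row are flat, and 650 mg is 21.7 mg/kg at the protocol's reference child and more for any lighter child. The upper bound on those affected is the 11 enrolled children. Actual exposure would also need a mild IAR and a site that followed the example without adjusting it.

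A reader might go further in two ways that the documents do not support.

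- **That the example is toxic.** No per-kg limit and no enrolled child's weight is given, so toxicity is not shown.
- **That the youngest children would get two to three times the reference per-kg amount.** That needs weights of 15 kg (650/15 = 43.3 mg/kg) down to 10 kg (650/10 = 65.0 mg/kg), which are tied to no enrolled child. Section 1.4.1 gives ages of "4.5 (2.10) years for subjects in the 3 mg/kg dose cohort", with four children. The youngest of four can then be at most 4.5 − 2.10/√4 = 3.45 years (ages 3.45, 3.45, 3.45 and 7.65 reproduce that mean and SD). So young children were enrolled, but turning an age into a weight needs growth data from outside the documents.

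Confidence is high that the amounts are unscaled and low on any child's actual mg/kg.

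**What to change.** In the mild row of Table 9, delete both example amounts and keep the instruction for oral antihistamine and antipyretic pre-treatment about 1.5 hours before the next infusion. Then add: *per local pediatric weight-based dosing, not exceeding the local maximum*. This brings the row into line with the amount-free wording of the row below and adds the missing weight basis. Weight is already measured for study-drug preparation, so no new data are needed.

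SAP Section 4 records that the sponsor decided on 11 July 2017 to stop the development program. A site notice is therefore needed only if any child is still being dosed; otherwise, correct the line before the table is reused.

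The cost is a one-line edit and the loss of a printed example. Sample size, endpoints and analyses are unchanged.

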7.2 Handling of Safety Parameters

7.2.1 Serious Adverse Events and Infusion-Associated Reactions (Immediately reportable to the Sponsor)

All SAEs and all IARs (serious and non-serious), irrespective of the treatment received by the subject, must be reported to the Sponsor or designee immediately and no later than 24 hours of the Investigator's first knowledge of the event (expedited reporting).

The definition and reporting requirement are in accordance with ICH Guideline for Clinical Safety Data Management, Definitions and Standards for Expedited Reporting (Topic E2, 1995).

7.2.3 Treatment and Follow-up of Adverse Events

During the study, all AEs and SAEs will be followed up until they have returned to baseline status or stabilized or until the Investigator and Sponsor or designee agree that follow-up is no longer necessary. If a clear explanation is established, it should be documented.

Treatment of AEs is at the discretion of the Investigator and should follow the standards of medical care at the Investigator's institution.

7.2.4 Follow-up of Abnormal Laboratory Test Values

In the event of unexplained clinically significant abnormal laboratory values, the tests should be repeated immediately and followed up until they have returned to baseline values and/or an adequate explanation of the abnormality is found. If a clear explanation is established, it should be recorded. All subject showing possible drug-induced liver injury should be evaluated by a hepatologist for other causes of elevated hepatic function tests and followed until all abnormalities return to normal or baseline, or are deemed not to be related to the study drug.

See Sections 5.2.1 and 6.2.1 regarding pausing rules for subjects with significantly elevated transaminases.

7.2.5 Pregnancy

Female subjects who are of childbearing potential at the time of consent or who become of childbearing potential during participation on study must agree to use a highly reliable method of birth control (expected failure rate less than 5% per year) for the duration of the study and for 30 days after the last dose of SBC-103.

Male subjects and their partners, must be using a highly reliable method of birth control (expected failure rate less than 5% per year) for the duration of the study and for 30 days after the last dose of SBC-103.

A female subject must immediately inform the Investigator if she becomes pregnant during the study and must not receive further SBC-103 infusions. Pregnancies occurring up to 90 days after the completion of the last infusion must be reported to the Investigator. The Investigator must report all pregnancies to the Sponsor within 24 hours of notification. The Investigator should counsel the subject discussing the risks of continuing with the pregnancy and the possible effects on the fetus. Monitoring of the subject should continue until conclusion of the pregnancy.

Pregnancy occurring in the partner of a subject participating in the study within 90 days of completion of the last infusion must also be reported to the Investigator and Sponsor. The partner should be counseled and followed as described above.

7.3 Recording of Adverse Events

At each contact with the subject (and the subject's parent or caregiver), the Investigator must seek information on AEs by specific questioning and, as appropriate, by examination. Information on all AEs should be recorded immediately in the source documentation and in the CRF. All clearly related signs, symptoms, and abnormal diagnostic procedures results should be recorded under one diagnosis.

Adverse events will be recorded from the time of signing of the informed consent until completion of the last scheduled visit, ie, the follow-up visit. Adverse events occurring after signing the informed consent but prior to the first dose of study medication will only be recorded if assessed as related to protocol procedures or requirements. Any AEs remaining unresolved should be recorded as ongoing. Ongoing AEs/SAEs should continue to be followed up for the period specified in Section 7.2.2 but without further recording in the CRF. However, follow-up information on SAEs must be reported to the Sponsor or designee as described in Section 7.4.1. Any SAE that occurs after the study period and is considered to be related or possibly related to the study treatment or study participation should be recorded and reported immediately.

Any AE that occurs within 24 hours of the infusion will be recorded by time and date. AEs occurring 24 hours after the infusion will be recorded by date only. The date and time, or the date when the AE started and stopped, as well as the intensity, seriousness, action taken with regard to SBC-103, causality assessment and outcome of the event will be recorded for each AE.

7.4 Reporting of Serious Adverse Events, Infusion-Associated Reactions and Unanticipated Problems

Investigators and the Sponsor must conform to the AE reporting timelines, formats and requirements of the various entities to which they are responsible. (§13 GCP-V; Detailed guidance on the collection, verification and presentation of AE/reaction reports arising from clinical trials on medicinal products for human use ['CT-3']; US CFR Title 21, §312.32, Investigational New Drug [IND] safety reporting). The Sponsor or designee will report all reportable events to all regulatory authorities, IECs or IRBs, and Investigators as required by local regulations.

All SAEs and IARs, and other reportable events (see Section 7.4.3) must be reported to the Sponsor or designee in an expedited manner according to timelines described in Section 7.4.1.

